### Research objectives:

1. To conduct a comparative assessment of the dynamics of nutritional deficiency and nutritional status of patients operated on for malignant tumors of the hepatopancreatoduodenal zone in the early postoperative period during isolated enteral, isolated parenteral and mixed types of nutritional support.
2. To analyze the dynamics of the state of protein and carbohydrate metabolism, the consistency of liver function in cancer patients operated on for malignant tumors of the hepatopancreatoduodenal zone, against the background of isolated enteral, isolated parenteral and mixed type of nutritional support in the early postoperative period.
3. To determine the degree of effectiveness of these methods of nutritional support in this category of patients based on the totality of the results of assessing nutritional status and the dynamics of the level of basal metabolism in these patients in the early postoperative period.

Researched 91 patients, will be divided into 3 groups:

1. The first group (n=31) included patients who received enteral nutrition (EN) after surgery.
2. The second group (n=30) included patients receiving parenteral nutrition (PN).
3. The third group (n=30) receiving mixed nutrition (MN), as is commonly considered the method of partial parenteral nutrition, in the early postoperative period.

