## **Methods of statistical data analysis**

All patients hospitalized for special treatment with a verified diagnosis of a malignant neoplasm were subjected to the study in the abdominal department of the KGP at the Regional Oncological Dispensary, Karaganda.

The quantitative and qualitative indicators obtained during the study were analyzed using descriptive and analytical statistics methods. For statistical processing of qualitative (diagnosis codes, dichotomous data) and quantitative variables: symptom intensity, severity, frequency of occurrence, we used the calculation of the median level (Me) with 25%-75% quartiles (Q25; Q75) and the calculation of the arithmetic mean (M) with error (m) and 95% confidence interval (95% CI), standard deviation (s). Quantitative variables were checked for normality of distribution using the Kolmogorov-Smirnov test, as well as the module of Skewness and Kurtosis for quantitative variables  $| \leq 2 |$ . Differences in the 3 groups of patients for quantitative variables corresponding to a normal distribution were identified using the Student's t test for unrelated groups, first for 3 or more groups, and then in pairs for each pair using the Student's t test. Differences for rank variables, or quantitative but not normally distributed for unrelated groups, were determined by the Kruskal-Wallis test or median test for 3 groups, and then pairwise or non-parametric Mann-Whitney test for each of the 3 pairs (groups 1 and 2, groups 1 and 3, groups 2 and 3), and for related groups (dynamic observations) by the Kendall test for 3 groups and then by the Wilcoxon test (Wilcoxon) for each of the 3 pairs (baseline, after 5 days and after 10 days).

Correlation was performed for quantitative variables according to Pearson and for rank variables according to Spearman. Statistical processing of the results was carried out using the Statistica program version 10.

**Results and discussion.** The nutritional status of patients in all three groups before surgery and during the 10-12 days of the postoperative period according to the methods of assessing nutritional status NRS, SGA and NRI was assessed as normal, moderate and severe malnutrition

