As can be seen from the presented data, in the preoperative period, according to the SGA assessment, 24 patients in the enteral group, 19 patients in the parenteral group, and 17 patients in the mixed group had normal nutritional status before surgery, with variations relative to patients with moderate to severe malnutrition. Assessment of nutritional status before surgery using the NRI scale allowed us to confirm the nutritional status of the vast majority of patients in all groups as relatively normal

Thus, in 62 of the 91 patients examined, the NRI was assessed as true negative (normal nutritional status), in 26 as true positive (moderate malnutrition), and in 3 as severe malnutrition. Data from the NRI method during this time period had a strong correlation with the results of the SGA scale ( $p < 0.005$ ).

On the 10-12th day of the postoperative period in patients of the “enteral” group, the results of the assessment on the SGA scale remained unchanged; according to the NRI rating scale, there was an increase in “moderate malnutrition” per patient (25%).

With parenteral nutritional support, 17 patients had “normal nutrition”, 14 patients had moderate malnutrition, with regression of “severe malnutrition” in 1 patient. In the mixed nutrition group, there was a complete elimination of signs of “severe malnutrition” by 100% according to the given scales ( $p < 0.005$ ).

In patients of all study groups, throughout the entire period of nutritional support, fluctuations in the level of basal metabolism were observed in average values of  $335.89 \pm 53.6$  kcal/day (13.44%) from the initial value - 1-2 days of the postoperative period and were due to variability body mass index and the dynamics of the temperature curve after surgery.

In patients in the groups with enteral and parenteral nutrition, by the end of these types of energy subsidies (days 10-15), the level of basal metabolism was observed to approach its initial values -  $2500.1 \pm 353.4$  kcal/day and  $2350.0 \pm 330.5$  kcal/day days accordingly. With a mixed type of nutrition, there was a statistically significant decrease in the level of basal metabolism by 6.78% ( $2250.0 \pm 105.2$  kcal/s), which allows us to conclude that patients' energy costs are more effectively covered with this option of nutritional support in a comparative aspect with isolated types nutrition ( $p < 0.03$ ).

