### **Conclusion:**

1. According to the NRI nutritional status assessment scales, the SGA mixed type of nutritional support at the time of transfer of patients to the specialized department and upon completion of this area of intensive therapy in the specialized department by 12-15 days of the postoperative period showed higher effectiveness in stabilizing the condition and maintaining the patients' caloric intake in a comparative aspect with the group of isolated enteral nutrition and parenteral nutrition.
2. Throughout the entire period of isolated enteral, parenteral and mixed nutritional support, all patients (100%) showed a relatively constant level of total blood protein.
3. In patients of all three groups, throughout the entire period of nutritional support, fluctuations in the level of basal metabolism were observed, which was due to the variability of body mass index and the dynamics of the temperature curve after surgery. In patients in the groups with enteral and parenteral nutrition, by the end of nutritional support (days 15-20), the level of basal metabolism was observed to approach its initial values. With a mixed type of nutrition, a statistically significant decrease in the level of basal metabolic rate was observed, which suggests a more effective coverage of the energy costs of patients with this option of replenishing nutritional ingredients.

**Researcher:** [name], PhD student KSMU

[contact].

e-mail: [contact].

[figure not shown]
Signature  17.03.2020

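### Conclusion 3 infers better energy coverage with mixed nutrition from a significant fall in one arm, with no change or interval given for the other two and no clear comparison of changes between arms

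*Combined protocol and SAP*

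**What the plan says.** The report has three arms: enteral (n=31), parenteral (n=30) and mixed (n=30). Basal metabolism is calculated by the Harris-Benedict equation from sex, age, weight and height (Clinical research program).

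The results text, which follows the statistical methods, makes three statements about it:

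- Over all groups it fluctuated on average by 335.89 ± 53.6 "kcal/day (13.44%) from the initial value - 1-2 days of the postoperative period".
- In the enteral and parenteral arms, by days 10-15, it came close to its initial values; a dash then introduces 2500.1 ± 353.4 and 2350.0 ± 330.5 kcal/day.
- "With a mixed type of nutrition, there was a statistically significant decrease in the level of basal metabolism by 6.78" per cent, to 2250.0 ± 105.2. A p<0.03 closes the clause that compares mixed nutrition with the isolated types.

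Conclusion item 3 repeats the pattern. For the isolated arms, "by the end of nutritional support (days 15-20), the level of basal metabolism was observed to approach its initial values". For the mixed arm it reports a significant decrease and reads this as more effective coverage of energy costs.

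For normally distributed data the methods section names "Student's t test for unrelated groups, first for 3 or more groups" and then pair by pair. For related observations over time it names the Kendall and Wilcoxon tests, at baseline, 5 days and 10 days. It lists 95% confidence intervals among the summaries.

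**The concern.** A significant change in one arm, next to arms described as close to where they began, does not show that the arms changed differently. That needs an estimate of the difference in change, with its uncertainty. Here the reader cannot see the change in either isolated arm, so neither half of the contrast can be weighed against the other.

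The arms also differ in how much they can show. The printed spread is 353.4 and 330.5 kcal/day in the isolated arms against 105.2 in the mixed arm. The same percentage fall is therefore easier to detect in the mixed arm.

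Research objective 3 rests partly on the dynamics of basal metabolism, so the inference bears on a stated objective.

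**Working it through.** **The plan's own figures.** No power, alpha or margin is stated, so there is none to reproduce. The p<0.03 cannot be rebuilt, because no arm's initial mean or SD of change is printed. Two rough checks, taking ± as an SD:

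- *Within the mixed arm.* Initial value 2250.0/(1 − 0.0678) = 2413.6; fall 163.6. Unpaired, t = 163.6/(105.2 × √(2/30)) = 6.0, p about 1e-7. This satisfies p<0.03 but is far smaller.
- *Between arms on the printed values, if all are end values.* Mixed against enteral: difference 250.1, p about 0.0004 to 0.0006. Mixed against parenteral: difference 100.0, p about 0.12.

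Neither check settles what p<0.03 refers to.

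**Chance of missing a 6.78% fall in an isolated arm.** Assumptions: ± is an SD, the SD is the same at both times, the printed values are end values, and alpha is 0.05 two-sided. Write r for the correlation between a patient's initial and end values. Power is from the noncentral t distribution, with SD of change = SD × √(2(1 − r)).

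- Enteral: 2500.1/0.9322 − 2500.1 = 181.8 kcal; 181.8/353.4 = 0.51 SD; n=31.
- Parenteral: 2350.0/0.9322 − 2350.0 = 170.9 kcal; 170.9/330.5 = 0.52 SD; n=30.

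| Test | Enteral missed | Parenteral missed |
|---|---|---|
| Unpaired | 49% | 50% |
| Paired, r=0.5 | 21% | 22% |
| Paired, r=0.7 | 5% | 6% |
| Paired, r=0.9 | near 0 | near 0 |

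In the mixed arm (163.6/105.2 = 1.56 SD) the miss rate is under 0.1% throughout. If the target is instead 6.78% of the printed values (169.5 and 159.3 kcal), the isolated-arm rates rise to about 54-55% unpaired and 27-28% at r=0.5. These targets ask what would happen under the same relative fall; they do not estimate the true starting levels. If ± were a standard error, power would be far lower.

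**What the printed figures imply, on one reading.** Suppose 2500.1 and 2350.0 are end values and 13.44% refers to the mean initial value of all 91 patients.

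- Overall initial mean: 335.89/0.1344 = 2499.2.
- Isolated arms, initial: (91 × 2499.2 − 30 × 2413.6)/61 = 2541.2.
- Isolated arms, end: (31 × 2500.1 + 30 × 2350.0)/61 = 2426.3.
- Pooled fall: about 115 kcal/day; 115/2541.2 = 4.5%.
- Gap to the mixed arm: 163.6 − 115.0 = about 49 kcal/day.

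The standard error of the gap is about √(2(1 − r)) × √(43.8² + 19.2²), where 43.8 = √(31 × 353.4² + 30 × 330.5²)/61 and 19.2 = 105.2/√30. Approximate 95% limits for the gap are −45 to 142 at r=0.5 and 7 to 91 at r=0.9.

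**Other readings.**

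- If 2500.1 and 2350.0 are initial values, as the dash allows, no change in the isolated arms can be derived. The percentage does not exclude this, since 335.89/2500.1 = 13.435%, which also rounds to 13.44%.
- If every arm started at 2499.2, the mixed arm fell by (2499.2 − 2250.0)/2499.2 = 10.0%, which contradicts the printed 6.78%.

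**Timing.** The results text places the end of support at days 10-15, and Conclusion item 3 at days 15-20. Weight, the input that changes, was measured before surgery and on days 5, 10 and 15.

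**The case against.** The strongest reply is that a before-after change within an arm is a related observation, for which the methods section names related-samples tests. Basal metabolism computed from sex, age, height and weight should correlate highly within a patient over two weeks. At r=0.9 a 6.78% fall would hardly ever be missed. This stands. A reader might infer that such a fall would be missed about half the time in the isolated arms, but that needs an unpaired test or a correlation near zero. An unpaired analysis cannot be excluded, because the only t test named is the one for unrelated groups, but the documents do not say that it was used here.

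A reader might also infer that the report's own figures show both isolated arms fell by 4.5%. They do not. The figure is a pooled back-calculation, cannot be split by arm, and depends on how one ambiguous sentence is read. Nor do the documents show that the pattern is merely a difference in spread: on that same reading with r=0.9, the mixed arm's larger fall may be real.

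Three further points are fair. The report claims that levels approached their initial values, which is weaker than a return to them. A level 4.5% away after fluctuations of 13.44% could be so described, and an equivalence margin chosen now would be post hoc. The p<0.03 may be a between-arm result, in which case some comparison was made. And figures are missing from the copy reviewed, so arm baselines may be shown there.

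None of this supplies a change and interval for the isolated arms in the text, or an identified between-arm comparison of change behind the conclusion.

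**Conclusion.** The inference of more effective energy coverage in Conclusion item 3 is not supported as written. The text gives no initial mean, change, p-value or interval for the isolated arms, and the status of both the printed means and p<0.03 is unclear. This needs no assumption beyond reading the text.

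The size is conditional. With ± as an SD, the chance of missing a 6.78% fall in an isolated arm lies between about 50% and near zero, depending on the test and the unreported correlation; the lower end is more plausible for a calculated quantity. The pooled 4.5% fall holds on one reading only. High correlation does not rescue the sentence on that reading: approximate 95% limits for the pooled fall (115 ± 1.96 × 43.8 × √(2(1 − r))) are 29 to 201 kcal/day at r=0.5 and 77 to 153 at r=0.9. The contrast may survive a proper analysis; the report does not show that it does. The point should be corrected, with medium confidence in the figures.

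**What to change.** In the results text:

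- Give each arm's initial mean, end mean and paired mean change with a 95% CI, at one stated time point. Reconcile days 10-15 with days 15-20.
- Say whether ± is an SD or a standard error, whether 2500.1 and 2350.0 are initial or end values, and which comparison p<0.03 belongs to.
- Reconcile 335.89 kcal (13.44%) with the arm means.
- Compare the changes between arms directly, for example by ANCOVA on the end value adjusted for the initial value, with 95% CIs for mixed against enteral and mixed against parenteral.

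In Conclusion item 3, keep the contrast only if those between-arm intervals support it. Otherwise state the observed change and CI for the isolated arms and drop the inference of more effective coverage. Do not add an equivalence margin after the fact.

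The cost is a small re-analysis of existing data and the rewording of one conclusion, which may come out weaker.

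### Conclusions 1 and 3 rank mixed feeding above enteral and parenteral feeding without a baseline-adjusted between-group difference, and the printed basal metabolism values do not show superiority over parenteral feeding

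*Combined protocol and SAP*

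**What the plan says.** **Conclusions.** Conclusion 1 says that on NRI and SGA mixed feeding "showed higher effectiveness in stabilizing the condition". It extends this to maintaining "caloric intake in a comparative aspect with the group of isolated enteral nutrition and parenteral nutrition". Conclusion 3 says that with mixed feeding "a statistically significant decrease in the level of basal metabolic rate was observed, which suggests a more effective coverage of the energy costs".

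**Results and discussion** (in the report, under Methods of statistical data analysis). For the isolated groups, "by the end of these types of energy subsidies (days 10-15), the level of basal metabolism was observed to approach its initial values": 2500.1 ± 353.4 (enteral) and 2350.0 ± 330.5 (parenteral). For mixed feeding, "there was a statistically significant decrease in the level of basal metabolism by 6.78" per cent, to 2250.0 ± 105.2. The sentence ends with a comparison to the isolated types and p<0.03. The disappearance of severe malnutrition in the mixed group carries p<0.005.

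**Analysis sections.** Protocol section III.2 names Student's t-test and Pearson correlation. The report lists t, Kruskal-Wallis or median, Mann-Whitney, Kendall and Wilcoxon tests. Neither mentions adjustment for baseline. The one confidence interval listed is for a mean.

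**Basal metabolism.** Protocol section III.1 and the report's Clinical research program say it was calculated by Harris-Benedict from gender, age, weight and height.

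**Design.** Protocol section V.1 speaks of random selection of patients. Section III.1 describes a prospective parallel study combined with a retrospective analysis.

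**The concern.** A significant change within one group does not show that the group differs from the others. The available text describes no way of assigning patients to the three groups, so the groups may have differed before feeding began. An unadjusted comparison of end values can then mistake a starting gap for an effect of feeding, or hide an effect.

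Conclusion 3 has a second weakness. Over days, weight is the only listed input to the formula that can move much. Even a genuine group difference in the calculated value would describe weight, and would not show how well energy costs were met.

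At stake is the report's main message: which feeding method is better, and against which comparator.

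**Working it through.** **1. Reproducing p<0.03.** The contrast is not stated, so the printed means were tested with Welch's t. Inputs: enteral 2500.1 ± 353.4, n=31; parenteral 2350.0 ± 330.5, n=30; mixed 2250.0 ± 105.2, n=30, taken as end values.

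*± read as SD.* SE of a difference = √(s₁²/n₁ + s₂²/n₂).

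| Contrast | Difference (kcal/day) | SE | t (df) | 95% CI | p |
|---|---|---|---|---|---|
| Mixed - enteral | -250.1 | √(105.2²/30 + 353.4²/31) = 66.3 | -3.77 (35.4) | -384.7 to -115.5 | 0.0006 |
| Mixed - parenteral | -100.0 | √(105.2²/30 + 330.5²/30) = 63.3 | -1.58 (34.8) | -228.6 to 28.6 | 0.12 |

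The three-group ANOVA gives F(2,88)=5.89, p=0.004.

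*± read as SE.* SE of a difference = √(SE₁² + SE₂²). Mixed minus enteral: √(105.2² + 353.4²) = 368.7, CI -998 to 498, p=0.50. Mixed minus parenteral: √(105.2² + 330.5²) = 346.8, CI -804 to 604, p=0.77. This reading implies an enteral SD of 353.4 × √31 ≈ 1968 kcal/day, so SD is the more plausible one.

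On neither reading do the printed values separate mixed from parenteral feeding.

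**2. Can the starting gap be recovered?** The pooled isolated end mean is (31 × 2500.1 + 30 × 2350.0)/61 = 2426.3, so the end gap is 2250.0 - 2426.3 = -176.3. A 6.78% fall to 2250.0 implies a mixed start of 2250.0/0.9322 = 2413.6. The isolated start depends on the reading:

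- *Isolated groups back at their starting values.* Start ≈ 2426.3, gap 2413.6 - 2426.3 = -12.6, about 13 kcal/day.
- *The all-patient figure of 335.89 "kcal/day (13.44%) from the initial value" taken as a share of the all-patient starting mean.* 335.89/0.1344 = 2499.2. Isolated start = (91 × 2499.2 - 30 × 2413.6)/61 = 2541.2, gap about -128 kcal/day.

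So between about 13 and about 128 of the 176 kcal/day could have been there at the start. The second reading is fragile: 335.89/2500.1 also rounds to 13.44%, so the base could be the enteral figure. It also needs a fall of about 115 kcal/day (2541.2 - 2426.3) in groups said to have approached their initial values.

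**3. Baseline status on SGA.** Normal before surgery: enteral 24/31 (77%), parenteral 19/30 (63%), mixed 17/30 (57%). Enteral minus mixed is 20.8 points (95% CI -2.3 to 43.8; Fisher p=0.11). The mixed group had the lowest share of normal patients.

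**4. Text against text.**
- Fluctuations in basal metabolism are called "due to the variability of body mass index and the dynamics of the temperature curve after surgery", but temperature is not a listed input of the formula.
- Conclusion 1 claims better-maintained caloric intake. Intake is not among the measures in the section III study plan, section III.1 or the Clinical research program.
- Parenteral follow-up counts are 17 normal + 14 moderate = 31, in a group of 30.
- Results place the end of support at days 10-15. Conclusion 3 has "by the end of nutritional support (days 15-20), the level of basal metabolism was observed to approach its initial values". The last scheduled weight is day 15.

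**The case against.** **A between-group test may have been done.** The report lists three-group and pairwise tests, and p<0.03 closes a sentence comparing mixed with isolated feeding. This stands. A reader might infer that the ranking rests only on within-group p-values; the documents do not establish that. They fail to identify the contrast and give no estimate with an interval.

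**Displays may be missing.** The results refer to presented data, and figures are absent from the text available here. Starting values, follow-up counts or intervals may have been shown there. NRI and SGA were also scheduled for day 15, so the reference to days 12-15 in Conclusion 1 may rest on data not visible here. This limits the point to the available text. A display would not add the baseline adjustment that neither analysis section names, nor make a weight-based formula a measure of energy coverage.

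**The starting gap may be small.** A reader might infer from the printed percentages that most of the end gap existed before feeding. The documents do not support that: if the isolated groups returned to their starting values, the gap was only about 13 kcal/day. The difference in change would then be about -164 kcal/day (2250.0 - 2413.6, against no change), with p about 0.02 even at zero within-patient correlation, assuming equal SDs at start and end. Adjustment could therefore favour mixed feeding.

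**The malnutrition result.** A reader might also infer that p<0.005 is impossible because NRI found only three severe cases in 91 patients. SGA may have supplied further changes, and a test across several times may have been used, so the fault is that test and contrast are unnamed.

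**Conclusion.** The point stands in this form: the ranking in Conclusions 1 and 3 goes further than the available results. With ± as SD and the printed figures as end values, the data favour a lower calculated basal metabolism than under enteral feeding (-250 kcal/day, CI -385 to -116). They do not show a difference from parenteral feeding (-100, CI -229 to 29). With ± as SE, neither contrast is significant. If the two isolated-group figures are starting values, the comparison cannot be rebuilt.

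These are unadjusted contrasts, and the starting gap cannot be recovered. The findings do not show that mixed feeding is no better; the direction in which adjustment would move the ranking is unknown.

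Two inferences fail whatever the contrasts show: energy coverage cannot be read from a fall in a calculated, weight-driven value, and better caloric intake is claimed without a listed intake measure.

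**What to change.** On data already held:

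- **Continuous outcomes.** Report starting values by group. Give mixed-minus-enteral and mixed-minus-parenteral differences with 95% CI adjusted for the baseline value (for example ANCOVA), at time points that match the conclusions. With about 30 patients per group, use operation type only in a sensitivity analysis.
- **NRI and SGA.** Tabulate baseline against follow-up category by group, compare groups taking baseline category into account, and correct the count of 31 in a group of 30.
- **Labelling.** State whether ± is SD or SE, and name the test and contrast behind p<0.03 and p<0.005.
- **Basal metabolism.** State the full formula, including any temperature term, and show weight change by group beside it.
- **Conclusions 1 and 3.** Limit them to what the between-group intervals support, separately against enteral and parenteral feeding. Drop the energy-coverage inference. Remove the caloric-intake claim unless intake was recorded and is reported. Reconcile days 10-15 with days 15-20.

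Cost: a modest re-analysis and rewording, with a degree of freedom or two for covariates and no new patients or measurements. The ranking may change in either direction.
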